#### Oxytocin and Vasopressin Effects and Evidence Supporting Efficacy of Low Dose

Oxytocin: Vasopressin and oxytocin are molecularly similar and there is some overlap in receptor occupancy. As vasopressin (V1a) acts to increase behavioral activation and can lead to aggression and irritability, occupation and thus activation of vasopressin receptors by oxytocin, could theoretically lead to increased aggression and irritability. Increased aggression and irritability could be exacerbated in individuals with PWS who are known to have genetic lesions of the oxytocin system. This also raises issues over ligand selectivity [90]. Oxytocin and vasopressin are structurally related analogs that differ by only two amino acids and share an evolutionary history. They also lack absolute receptor subtype selectivity and their receptor subtype selectivity is always relative and concentration dependent. Selectivity may be defined on the basis of the binding affinity of the ligand. To be "selective" on one receptor subtype, a ligand's affinity constant on the other receptor subtypes should be at least two orders of magnitude higher. Thus, we posit that the increase in the number of temper outbursts observed in the Einfeld study [72] could have been caused by ligand promiscuity. Higher concentrations of oxytocin may have overwhelmed the OXT-R subtype and spilled over to bind with vasopressin receptors, an event that could have led to the observed increased aggression and irritability. This is particularly likely in the PWS population, a population known to have abnormal oxytocin production. Using the lower dose of 16 IU gd in our study replicates the dose that yielded positive findings in children with PWS by [name] and addresses this issue. Converging biological and behavioral evidence suggests that lower OXT doses may be more efficacious than higher doses. For instance, compared with higher doses, lower doses increased peripheral levels of OXT in saliva [65] attenuated cortisol stress responses [66] and increased eye gaze in patients with Fragile X syndrome [67]. In animals, a low dose of OT administered shortly after birth increased partner preference later in life, whereas higher doses did not [68]. Similarly, lower doses have been associated with stronger increases in social recognition compared with higher doses [69,70]. The dose-response data reported for reduction of anger in response to ambiguous faces in healthy controls in low dose vs high dose IN OXT also supports the selected dose of the study.

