#### Preliminary Study 4: Ongoing Pilot Study of IN-OXT/Placebo in Childhood PWS:

Our current pilot study of an 8-week randomized placebo-controlled double-blind trial of 16 IU/day of IN-OXT in children and adolescents with PWS is ongoing and blinded. To date, over a 3 month time period, we have enrolled 12 pediatric PWS subjects, and randomized 9 subjects. We aim to randomize 24 subjects. Although the data remain blinded at this time, we briefly describe reports of efficacy and side effects observed in the study thus far. The only AE noted in 1 blinded subject was polyuria/nocturia, of mild severity, and possibly related to study drug. Subjects on the blinded 16 IU/day of IN-OXT/placebo dose were noted to have the following responses by parent report to study clinician: 1. improvements in hyperphagia- "for the first time left food on the plate", "best Thanksgiving ever", "less asking for food", "less freak-outs around food"; 2. improvements in compulsivity- "better able to transition and switch to another topic other than food", "less compulsive questioning", "less skin picking", "less need for control", "less restricted interests in stuffed animals"; and 3. improvements in other behaviors- "less anxiety", "less tantrums", "more verbal utterances"," longer string of words", and "more back and forth banter". Of note, the study has not been complicated by unmasking of medical co-morbidities. There have been no tolerability or safety issues to date. Subjects have not required downward titration or had worsening of laboratory parameters to date.

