Psychiatric Interview	30 min	Parent/Child/Cli nician	х						
Intelligence Test	60 min	Clinician/ Child		Х					
Randomization	0 min			Х					
Concomitant Medications	5 min	Parent/Child/Cli nician	х	х	х	x	х	х	Х
Adverse Events/Monitoring for hypogonadism, sleep apnea, lethargy	10 min	Parent/Child/Cli nician	x	х	x	x	x	х	x
Standard Laboratory Tests*	10 min	Clinician/ Child	X***	Х				Х	
Hormone and Metabolic Laboratory Tests**	10 min	Clinician/ Child		х				х	
Treatment Given	10 min	Parent/Child/Cli nician		х		x		х	
Urine Pregnancy Test (if appropriate)	5 min	Child/Clinician	х	Х				х	
Vital signs	15 min	Clinician/ Child		Х				Х	
Eating Behavior Measures									
Hyperphagia Questionnaire- Clinical Trials (HQ-CT)	15 min	Parent/Child/Cli nician	х	х	x	x	х	x	х
Weight, Body Composition and BMI	5 min	Parent/Child/Cli nician		х				х	
Dietary Diary ASA24 Automated Self-	15 min	Parent		х				х	

Administered 24 Hour Recall									
Repetitive Behavior Measures									
Montefiore-Einstein Rigidity Scale –Revised (MERS-PWS)	15 min	Clinician		х		х		x	х
RBS-R	15 min	Parent		X [pre-dose]		х		x	х
Oxytocin Measures									
Salivary Oxytocin Levels	10 min	Clinician/Child		X [pre- and 1 hour post dose]		X [pre- and 1 hour post dose]		X [pre- and 1 hour post dose]	x
Global Clinical Improvement and Quality of Life Measures									
ABC-I (Full ABC will be completed to measure this subscale)	25 min	Parent		X [pre-dose]	х	х	х	x	х
CGI-I	5 min	Clinician			X	Х	Х	Х	Х
CGI-S	5 min	Clinician	Х	Х					
WHOQOL	20 min	Parent/Child/ Clinician		Х		х		x	х
Caregiver Strain Questionnaire	10 min	Parent		Х		Х		Х	х

\* Standard Laboratory Tests: CBC, CMP including sodium, IGF-1, thyroid panel, lipid panel, hemoglobin A1C, and urine pregnancy test
 \*\* Hormone and Metabolic Laboratory Tests: testosterone, estrogen, growth hormone, ghrelin, pancreatic polypeptide, peptide YY, leptin, GLP-1, insulin, glucagon

\*\*\* To be done at local Quest

Table 2: Intranasal Oxytocin vs. Placebo for the Treatment of Hyperphagia in Prader-Willi Syndrome SCHEDULE OF EVENTS

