These 3 categories are based on the Site Investigator's clinical judgment, which in turn depends on consideration of various factors such as the subject's reports, the physician's observations and the physician's prior experience. The severity of the AE should be recorded in the source documentation. The evaluation of severity is distinguished from the evaluation of "seriousness." A severe event might not meet the criteria for seriousness and a serious event might be evaluated as mild.

**Safety Analyses:** Safety will be evaluated from concomitant medications, study drug exposure, treatment emergent adverse events, serious adverse events, death, suicidal ideation, physical examinations, clinical laboratory test results and vital signs. All summaries of adverse events and suicidal evaluation will be presented. Serious adverse events, deaths (if any), abnormal laboratory results and abnormal vital signs will be listed in patient listings. All AEs will be coded by the system organ class (SOC) and preferred term (PT) using the Medical Dictionary for Regulatory Activities (MedDRA).

Non-treatment emergent AEs are defined as

- AEs that started and resolved prior to the first study drug dosing
- AEs that started prior to the first study drug dosing, resolved after first study drug dosing and the grade remained the same or reduced.

Treatment emergent adverse events (TEAEs) are defined as all AEs that begin or worsen after the patient receives the first dose of the study drug until follow –up. All reported AEs (including non-treatment-emergent adverse events) will be listed. Overall summary of TEAEs, such as total number of reported TEAEs, total number of patients reporting at least one TEAE, severity of TEAEs, relation to study drug, serious AEs, any deaths, TEAEs leading to study drug discontinuation, will be summarized by treatment group. In addition, TEAEs will be tabulated by SOC and PT. A table will contain the number of TEAEs (frequency of occurrence, number and percentage of patients) by treatment group will be created.

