  - *b.* The effects of treatment on frequency and severity of repetitive behaviors will be assessed by fitting linear mixed effects models to the data on the MERS-PWS scores. We hypothesize that IN- OXT will significantly reduce repetitive behaviors from baseline to endpoint compared to Placebo.
- 2. Secondary Aim (2) Weight, BMI (z-score) and body composition via bioelectrical impedance analysis
  - a. Weight and BMI (z-score) will be measured at each visit. It will be utilized to evaluate whether IN-OXT significantly modulates energy metabolism and reduces weight compared to placebo. Body composition via impedance analysis will be measured at baseline and endpoint.
- 3. Secondary Aim (3) Quality of Life Measures
  - a. The relationship between quality of life and treatment will be assessed using scores on the WHOQOL. We hypothesize that IN-OXT will improve quality of life from baseline to endpoint as measured by an increase in overall score on the WHOQOL from when compared to placebo.
  - b. The relationship between caregiver strain and treatment will be assessed using scores on the CSQ. We hypothesize that IN-OXT will caregiver strain from baseline to endpoint as measured by an reduction in overall score on the WHOQOL from when compared to placebo.
- 4. Secondary Aim (4) Salivary Oxytocin Levels
  - a. Both group and individual differences in salivary OXT concentration will be measured. Correlations between individual salivary OXT concentrations at day 1 and weeks 4 and 8 as well as correlations between OXT and changes in our primary outcome measure, hyperphagia assessed by the [name] Hyperphagia Questionnaire, will be evaluated using the Spearman rank or Pearson correlation. Additional correlation analysis will be performed on salivary oxytocin levels and secondary outcome measures: RBS-R, WHOQOL and CGI-I. We hypothesize that higher concentrations of salivary oxytocin will be correlated with positive changes on each outcome measure, indicating improvement in symptoms.
- 5. Secondary Aim (5) Safety Analyses
  - a. Rates of specific side effects and other adverse events will be tabulated and compared between treatment groups using the chi-square test. Please see the section labeled "Safety Analyses" for further details on how adverse events will be monitored and rated.

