  - b. The relationship between frequency of suicidal behaviors will be assessed on the ABC-I to evaluate whether IN-OXT vs. placebo is associated with a change in the irritability subscale of the ABC-I which serves as a surrogate for suicidal ideation in this population.

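### For standard laboratory tests and vital signs the safety analysis specifies only a listing of abnormal values; by-arm summaries of the scheduled baseline and week-8 values should be added.

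*Combined protocol and SAP*

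**What the plan says.** The Safety Analyses paragraph, under Assessment of Safety, says safety will be evaluated from several sources, among them "suicidal ideation, physical examinations, clinical laboratory test results and vital signs". It then assigns outputs. For adverse events and suicidality, "All summaries of adverse events and suicidal evaluation will be presented". For the laboratory and vital-sign data, "abnormal laboratory results and abnormal vital signs will be listed in patient listings". The tables described after that are by treatment group, but they concern treatment-emergent adverse events only.

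In the Detailed Description of Analyses, Secondary Aim (5) names two items. The first is "Rates of specific side effects and other adverse events will be tabulated and compared between treatment groups using the chi-square test". The second asks whether "IN-OXT vs. placebo is associated with a change in the irritability subscale of the ABC-I".

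Table 2 schedules vital signs at baseline and week 8, and the standard laboratory tests at screening, baseline and week 8. Its footnote defines the latter: "Standard Laboratory Tests: CBC, CMP including sodium, IGF-1, thyroid panel, lipid panel, hemoglobin A1C, and urine pregnancy test". The Objective paragraphs under Specific Aims and Approach both state that the effects of IN-OXT on safety measures will be compared from baseline to week 8. Exploratory aim 4 compares a set of hormones between arms and looks at change in HbA1c.

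**The concern.** The objectives promise a comparison of safety measures, and the analysis section never says how it will be made for the standard laboratory tests and vital signs. What it does specify depends on each value crossing a limit, and the limit is not defined for children aged 5 to 17. Inclusion criterion 9 requires laboratory results within the normal range for individuals with PWS, so a moderate drug effect on a laboratory variable would mostly stay inside that range and would not enter a listing.

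At stake is what a Phase 2 trial meant to inform Phase 3 can say about these variables. A listing gives no estimate of the drug-placebo difference and no interval around it, although the values needed for both are scheduled to be collected.

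**Working it through.** **1. Which output covers which data**

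| Data | Scheduled baseline and week 8 | By-arm output specified |
|---|---|---|
| Adverse events | recorded throughout | Tables by arm; chi-square on rates |
| ABC-I | yes | Arm comparison, Secondary Aim (5) |
| Hormones named in exploratory aim 4, HbA1c | yes | Comparison of change (hormones); changes in HbA1c examined |
| Sodium and other chemistry, CBC, lipids, thyroid, IGF-1 | yes | None; abnormal values listed |
| Vital signs | yes | None; abnormal values listed |

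**2. The plan's own power figure**

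The Power Analysis paragraph gives 25 per group, a two-sample t-test, two-sided 5%, and 80% power at d = 0.8. The normal approximation gives 80.7% and the noncentral t gives 79.1%. The figure reproduces, and 79.1% is carried forward.

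**3. What a listing can show, compared with means**

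The documents give no SD, reference limit or relevant shift for any of these variables, so the illustration is in SD units. Assumptions: normal values with equal SD, placebo mean at zero, abnormal meaning below −L, and a downward shift s on drug. No by-arm test of abnormal laboratory counts is planned. The uncorrected chi-square is used because it is the test the plan names for safety rates, which treats the listing generously.

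- P(abnormal, placebo) = Φ(−L); P(abnormal, drug) = Φ(−L + s); expected count = 25 × P.
- Example, L = 2 and s = 0.8: Φ(−2) = 0.0228, × 25 = 0.57; Φ(−1.2) = 0.1151, × 25 = 2.88.
- Chi-square power is the sum of the binomial probabilities of all pairs of counts with p ≤ 0.05.

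| L (SD) | s (SD) | Expected abnormal, drug vs placebo | Chi-square on counts | t-test on means | P(no treated child listed) |
|---|---|---|---|---|---|
| 1.645 | 0.8 | 5.0 vs 1.25 | 38% | 79% | 0.4% |
| 2.0 | 0.8 | 2.9 vs 0.6 | 20% | 79% | 5% |
| 2.5 | 0.8 | 1.1 vs 0.2 | 2% | 79% | 32% |
| 1.645 | 0.5 | 3.2 vs 1.25 | 14% | 41% | 3% |
| 2.0 | 0.5 | 1.7 vs 0.6 | 5% | 41% | 18% |
| 2.5 | 0.5 | 0.6 vs 0.2 | 0.2% | 41% | 56% |

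**4. Baseline adjustment and missing values**

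With an assumed baseline to week-8 correlation of 0.5, the residual SD is √(1 − 0.25) = 0.866. The effective shift becomes 0.8/0.866 = 0.92 SD (power 89%) or 0.5/0.866 = 0.58 SD (power 52%).

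The Missing data paragraph expects little loss but gives no rate. At an assumed 10% or 20% loss, the unadjusted t-test power at 0.8 SD falls to 75% or 69%.

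**5. What the added summary would deliver**

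The 95% interval for a difference in means has a half-width of 2.0106 × √(2/25) = 0.57 SD. That is wide, but it is an estimate with stated uncertainty.

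**The case against.** The strongest reply is that a comparison is already intended. Both Objective paragraphs promise to compare safety measures, and the secondary analyses, which list safety, are to use methods similar to those of the primary analysis. This is right as far as it goes. A reader might infer that an arm-level shift in sodium or vital signs would go unreported; the documents do not support that. The by-arm output is unspecified, not ruled out. But where the safety aim is set out in detail, it names neither laboratory tests nor vital signs.

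It would also be wrong to say that no laboratory variable is compared, given exploratory aim 4, or that both values will exist for every child. Special Circumstances and Missing data allow for gaps.

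A second tempting inference is that the protocol's pharmacology points to sodium. The section on vasopressin effects says "Higher concentrations of oxytocin may have overwhelmed the OXT-R subtype and spilled over to bind with vasopressin receptors", but the passage is about V1a receptors and aggression at higher doses than the starting dose here, and does not mention sodium or water balance. The pilot report, "The only AE noted in 1 blinded subject was polyuria/nocturia, of mild severity, and possibly related to study drug", concerns one child whose allocation was unknown. Neither supports a sodium mechanism, and the point does not need one.

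Third, the safety monitor reviews laboratory values at least monthly, and the monitoring committee may see unblinded data. These protect children during the trial but do not produce a by-arm result in the final report.

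Finally, the power contrast rests on assumed limits and shifts. That stands. The size of the gap moves with the assumptions, but the comparison of means does better in every row examined.

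**Conclusion.** The point holds as a gap in specification with a cheap remedy. For the standard laboratory tests other than HbA1c, and for vital signs, the plan names these data as part of the safety evaluation and schedules them twice on treatment-relevant visits, yet specifies only a listing of abnormal values.

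The listing is a weak instrument for an arm-level shift. At 0.8 SD, a count-based chi-square would detect it 38% to 2% of the time as the limit moves from 1.645 to 2.5 SD, against 79% for means. At 0.5 SD the figures are 14% to 0.2% against 41%. These rest on 25 per arm with complete data, normality, and assumed limits and shifts.

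The gap does not affect the primary analysis or the sample size. The documents contain no rule by which laboratory safety would be declared acceptable from the listing, so no such conclusion should be attributed to the plan.

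**What to change.** In the Safety Analyses paragraph, keep the listing of abnormal values and add text along these lines:

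- For each standard laboratory test and vital sign, summarise baseline and week-8 values by arm, with the number of children contributing to each.
- Report the baseline-adjusted week-8 difference between arms with its 95% confidence interval.
- Give shift tables from baseline to week 8 by arm, using stated age- and sex-specific reference limits. The same limits then define abnormal for the listing.
- State that these are descriptive estimates, unadjusted for multiplicity.

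Secondary Aim (5) should refer to this output, so that the comparison promised in the objectives can be traced to a table.

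The cost is SAP wording and standard safety tables from data already scheduled. Visits, sample size and clinical rules do not change. The small downside is a number of unadjusted comparisons, in which some intervals will exclude zero by chance; reading them as estimates rather than tests deals with that.

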#### Independent Data Safety Monitoring Committee

An Independent Data Safety Monitoring Committee (DSMC) will review safety and clinical outcome data including data on adverse events (AEs) and serious adverse events (SAEs) at regular intervals. They will meet biannually to review study reports. The DSMC will be independent of the investigator and will be empowered to recommend stopping the study due to safety concerns, but not for efficacy or futility. The DSMC may review blinded, unblinded, or partially unblinded data, but the investigator will remain blinded until the official unblinding of the database.

**Statistical Analyses:** Analyses will be based on the intent-to-treat approach in which subjects are analyzed in the group to which they were originally assigned regardless of treatment compliance. All variables will be initially screened for inconsistent or abnormal values, and continuous measures will be assessed for skew and outliers. Transformations to improve normality will be applied when necessary. The demographic characteristics of all randomized patients will first be summarized using standard descriptive statistics (means, medians, standard deviations, and ranges for continuous variables and frequencies for categorical variables). Although subjects will be randomized 1:1 to the two treatment groups, imbalances in patient characteristics may still occur by chance given the limited sample size of the Phase 2 trial. Between group differences in the baseline demographic and other prognostic variables will be assessed using the chi- square test for discrete variables and the T-test or Wilcoxon rank sum test for continuous variables. Baseline characteristics which are found to be significantly different will be considered for inclusions as potential confounders in secondary analyses of treatment effects.

Summary of Analytic Approach: The primary outcome measure is change on the continuous measure of the Hyperphagia Questionnaire-Clinical Trials, a valid and reliable measure of the food seeking pathology in PWS. Secondary outcome measures include a measure of repetitive behavior (RBS-R and MERS-PWS), weight, measures of Quality of Life and Global Functioning (WHOQOL, CGI), and measures of salivary Oxytocin concentration. Given that these outcomes are all continuous variables, they will be analyzed using the same general statistical strategy as outlined below.

Measurements obtained at a specific time point (e.g. 8 weeks) will be compared between the IN-OXT and placebo groups with the two sample t-test or Wilcoxon rank sum test. In addition, the change in outcome measures between baseline and 8 weeks will be compared between

treatment groups. Exploratory analyses will first be performed to evaluate whether the magnitude of changes in these variables between the two time points depends on the baseline value. If there is no evidence that change is dependent on baseline, then two sample tests will be used to compare the mean change in each variable between treatment groups; otherwise, analysis of covariance models will be fit to the data where the outcome is the level measured at 8 weeks, and the main effects are treatment group and baseline value [15;37]. Adjustment for any patient characteristics which appear to be imbalanced across treatment groups will be accomplished by including the relevant terms as additional covariates into the model. To compare longitudinal trends in outcomes between treatment groups, linear mixed effects models will be fit to all repeated measures obtained during follow-up, with main effects for time and treatment group and a time x treatment interaction term; this is a widely used statistical approach in longitudinal studies of psychiatric outcomes. Appropriate data transformations, such as the log transform, will be applied if the data deviate from the normal distribution. Although a number of different outcomes will be analyzed, we will not adjust for multiple testing given the exploratory nature of this study.

Additional subgroup analyses will also be performed to evaluate and compare treatment effects in males and females. Given the limited sample size of this Phase 2 trial, however, any subgroup analyses will be viewed as exploratory.

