#### **Detailed Description of Analyses**

**Primary Analyses**: Analyses for Specific Aim (1): To compare IN-OXT vs. placebo with respect to improvement in the hyperphagia severity in children with PWS via improvement in scores on the Hyperphagia Questionnaire-Clinical Trials.

The primary analysis will evaluate the hypothesis that IN-OXT will decrease hyperphagia vs. placebo.

- 1. Response to treatment will be assessed in two ways:
  - a. The effects of IN-OXT on hyperphagia will be analyzed using an intent-totreat approach with the two-sample T-test or Wilcoxon rank sum tests to compare treatment groups at specific visits as well as linear mixed effects models to analyze the repeated measures and changes over time.
  - b. The proportion of responders in each treatment group will also be compared. Response will be defined as a 30% or greater decrease in food-seeking and eating behaviors from baseline on the Hyperphagia Questionnaire-Clinical Trials. Dropouts for clinical reasons will be coded as non- responders. Differences in the proportion of responders in each treatment group will be evaluated using the chi-square test and time to response will be assessed using survival analytic techniques.
  - c. All tests will be two-tailed with an alpha level of 0.05.

**Secondary Analyses:** Analyses for Specific Aims (2) through (8): To compare IN-OXT vs. placebo in children with PWS on change in:(2) Repetitive behaviors via scores on the Repetitive Behavior Scale – Revised (RBS-R) and Montefiore-Einstein Rigidity Scale-Revised (MERS-PWS)(3) Weight and body composition via impedance analysis. (4) Quality of Life Measures on the World Health Organization Quality of Life Scale (WHOQOL)(5) Clinical Global Impression Scale (CGI-I) (6) Salivary Oxytocin Concentration (7) Safety Analyses

IN-OXT and placebo groups will be compared to the above secondary measures will be analyzed using methods similar to those outlined above. Associations between outcome measures at a specific time point will be analyzed with the Spearman rank or Pearson correlation coefficient.

- 1. Secondary Aim (1) Repetitive Behaviors
  - *a.* The effects of treatment on frequency and severity of repetitive behaviors will be assessed by fitting linear mixed effects models to the data on the RBS-R scores. We hypothesize that IN- OXT will significantly reduce repetitive behaviors from baseline to endpoint compared to Placebo.

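### The plan gives two different rules for adjusting for chance baseline imbalance and does not say whether the adjusted or the unadjusted HQ-CT estimate is primary

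*Combined protocol and SAP*

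**What the plan says.** The opening paragraph of Statistical Analyses plans significance tests of baseline variables: "Between group differences in the baseline demographic and other prognostic variables will be assessed using the chi- square test for discrete variables", with a t-test or rank sum test for continuous ones. It then gives a use for them: "Baseline characteristics which are found to be significantly different will be considered for inclusions as potential confounders in secondary analyses of treatment effects". It names no variables to be screened and no significance level for the screening.

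The Summary of Analytic Approach follows. It defines the primary endpoint: "The primary outcome measure is change on the continuous measure of the Hyperphagia Questionnaire-Clinical Trials". After adding the secondary outcomes, it says of all of them that "they will be analyzed using the same general statistical strategy as outlined below". That strategy compares change scores between arms or, if change is found to depend on baseline, fits an ANCOVA in which "the outcome is the level measured at 8 weeks, and the main effects are treatment group and baseline value". The next sentence is: "Adjustment for any patient characteristics which appear to be imbalanced across treatment groups will be accomplished by including the relevant terms as additional covariates". It sets no threshold and does not limit the adjustment to secondary analyses.

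Under Detailed Description of Analyses, Primary Analyses, the HQ-CT methods are the "two-sample T-test or Wilcoxon rank sum tests to compare treatment groups at specific visits as well as linear mixed effects models", with the condition "All tests will be two-tailed with an alpha level of 0.05". No covariates are listed. Research Strategy And Feasibility says that randomisation is stratified by gender, but gender is not named as a covariate in the main analysis.

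**The concern.** Someone writing the analysis program would find two instructions for the same situation. Under the first, a variable matters if its baseline test is significant, it may then be included, and it goes into secondary analyses. Under the second, a variable matters if it looks imbalanced, it will be included, and it goes into the model just described. With no sentence ranking the adjusted and unadjusted HQ-CT estimates, the choice could be made with both results in view.

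Apart from the inconsistency, both triggers select on the wrong feature. In a randomised trial, between-arm baseline differences arise by chance. A covariate earns its place by predicting HQ-CT, and a baseline p-value says nothing about that. What is at stake is a clear primary result and some precision that could be had at no cost, in a trial with 80% power only at a large effect.

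This is separate from the plan's check on whether change depends on baseline HQ-CT, which concerns the outcome's own baseline value.

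**Working it through.** **The plan's own figure.** Power Analysis gives 25 per arm, d = 0.8, two-sided 5%, 80% power. With the noncentral t, the noncentrality is 0.8 × √(25/2) = 2.83 on 48 df, so power is 79.1%. The normal approximation gives 80.7%. The stated figure reproduces and is not in dispute.

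**The two rules side by side.**

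| | Statistical Analyses, opening paragraph | Summary of Analytic Approach |
|---|---|---|
| Trigger | significant baseline test, level not given | apparent imbalance, no threshold |
| Force | considered | will be done |
| Place | secondary analyses | the model |

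**How often each would be triggered.** The documents give neither the number of variables nor a threshold, so these are assumptions. For k independent tests at level a, the chance of at least one trigger is 1 − (1 − a)^k.
- At a = 0.05: k = 5 gives 1 − 0.95^5 = 23%; k = 8, 34%; k = 10, 40%; k = 15, 54%.
- Reading apparent imbalance as p < 0.20: k = 10 gives 1 − 0.80^10 = 89%.
- Reading it as a standardised difference above 0.25 (simulated): 91% to 98% for 5 to 8 variables.

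The two rules would therefore often select different covariates.

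**Effect on the test.** Trials of 25 per arm were simulated with independent normal covariates and total outcome SD 1, with power taken at d = 0.8.

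| | A: 10 covariates, 3 with r = 0.3 | B: 5 covariates, 1 with r = 0.3 | C: 8 covariates, joint R² = 0.3 |
|---|---|---|---|
| Apparent-imbalance trigger | p < 0.20 | p < 0.20 | std. difference > 0.25 |
| Power, unadjusted | 79% | 78% | 79% |
| Power, significance rule | 78% | within 1 point of unadjusted | 79% |
| Power, apparent rule | 77% | 76% | 80% |
| Power, covariates fixed in advance | 88% (the 3) | 81% (the 1) | 85% (all 8) |
| Type I error, either rule applied mechanically | between 4% and 5% | between 4% and 5% | 3.5% to 4.4% |
| Type I error, best of the three results | 7.1% | 5.8% | 7.1% |

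The three results in the last row are the unadjusted one and the two imbalance-adjusted ones. Varying setting C over 5 or 8 covariates and R² from 0.1 to 0.5, mechanical use gives 3.6% to 4.4% (significance rule) and 2.4% to 4.1% (apparent rule). Best-of-three gives 6.1% to 7.1%. Fixed covariates in C have a type I error of about 5.2%.

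**Check on the fixed-covariate power.** With k covariates jointly explaining R², the noncentrality is about 0.8/√(1 − R²) × √12.5 × √((48 − k)/48) on 48 − k df.
- One predictor, R² = 0.3² = 0.09: 0.839 × 3.536 × 0.990 = 2.93, power about 82%.
- Three predictors, R² = 3 × 0.09 = 0.27: 0.936 × 3.536 × 0.968 = 3.21, power about 88%.

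Both agree with the simulation to within a point.

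**The case against.** The strongest reply is that the two sentences are one plan: the first says when a covariate is considered and where it goes, and the second says how the adjustment is carried out. The Primary Analyses text is more specific and lists no covariates. The sentence on apparent imbalance follows a conditional ANCOVA, and the alternative two-sample tests take no covariates. On that reading the primary comparison is unadjusted. This is possible and may be what was meant, but no sentence makes the link, the triggers would still differ, and the shared strategy expressly covers the primary outcome.

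A reader might infer that the plan puts imbalance-chosen covariates into its main model, so that the data decide which HQ-CT result is the main one. The documents do not go that far. The second rule refers to the model without calling it primary, and the first rule mentions secondary analyses without saying that adjustment is confined to them.

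A reader might also infer inflated type I error. Neither rule does that when followed; both are slightly conservative. The 6% to 7% needs a choice of the best of three results, which neither sentence proposes.

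Nor should disagreement between results be counted as harm from the discrepancy. In setting A, the unadjusted and apparent-imbalance results fall on different sides of 0.05 in 12% of trials at d = 0.8, but the unadjusted and fixed-covariate results do so in 13%. At d = 0.5 the figures are 15% and 19%. In setting B the first figure is 7% at d = 0.8. Adjusted and unadjusted analyses of 50 patients differ about this often anyway.

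Finally, this is a Phase 2 trial that the plan calls exploratory, and it leaves other choices open, such as t-test or rank sum test, change score or ANCOVA, and single visit or mixed model. That limits the weight of the point. However, the exploratory label is used to justify making no multiplicity adjustment across outcomes, and it does not settle which HQ-CT estimate is primary.

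**Conclusion.** The point holds as an inconsistency of rule together with a weak method of choosing covariates. The two passages differ in trigger, force and place, and the primary analysis text does not say whether the adjusted or the unadjusted HQ-CT estimate counts.

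The direct cost is small. Followed mechanically, the rules keep type I error at or below 5% and change power at d = 0.8 by between a 2-point loss and a half-point gain (setting C, apparent rule: 79.4% to 80.0%). An open choice among three results would raise type I error to about 6% to 7%.

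The larger figure is the gain available from covariates fixed in advance: from about 78-79% power to 81% with one predictor at r = 0.3, or 88% with three. That gain belongs to prognostic adjustment in general. It does not measure damage done by the wording, and the documents do not establish how strongly any variable predicts HQ-CT change. Covariate number, independence, strength and the thresholds for apparent imbalance are all assumptions.

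The plan should be changed, because the change is cheap and removes the ambiguity.

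**What to change.** 1. In the Summary of Analytic Approach, delete the sentence on apparent imbalance as it applies to the main HQ-CT analysis.
2. State one primary HQ-CT model whose covariates are fixed before unblinding, on prognostic grounds and from variables already collected. Gender, as the stratification factor, and baseline HQ-CT are natural candidates. Say that the set does not depend on between-arm baseline comparisons.
3. In the opening paragraph of Statistical Analyses, keep the baseline tables descriptive and drop significance tests as a trigger for adjustment.
4. Label any model adjusted for observed imbalance a sensitivity analysis.

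This takes a few sentences of wording, with no new data and no change to the sample size. The one small drawback is that a chance imbalance in a variable not listed in advance is addressed only in a sensitivity analysis.
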